#### 9.1.2 Secondary Efficacy Endpoint

Secondary efficacy endpoints include the following:

- **EU and RoW:** Proportion of positive pruritus assessments at the subject level over the 24-week Treatment Period. A positive pruritus assessment is defined as a scratching score of  $\leq 1$  or at least a one-point drop from baseline on the Albireo ObsRO instrument. At each assessment, the AM score will be compared to the AM baseline, and the PM score will be compared to the PM baseline. Both AM baseline and PM baseline pruritus assessments will be included in the analysis of this endpoint. AM scores from the 14 days prior to the first dose of study medications will be averaged as AM baseline. PM scores from the 14 days prior to the first dose will be averaged as PM baseline.
- **US:** Proportion of patients experiencing at least a 70% reduction in fasting s-BA concentration from baseline to the end of treatment or reaching a level  $\leq 70$   $\mu\text{mol/L}$  compared to placebo after 24 weeks of treatment.
- **All Regions:**

All secondary endpoints are compared to placebo.

- Change from baseline to Week 12 and to Week 24 in fasting serum bile acids
- Change from baseline to Week 12 and to Week 24 in serum ALT concentration
- Change in growth from baseline to Week 12 and to Week 24
- Proportion of responders for pruritus scores at Weeks 12 and 24 based on the Albireo PRO and ObsRO instruments
- Change in sleep parameters measured with the Albireo PRO and ObsRO instruments from baseline over the 24-week Treatment Period
- Proportion of individual assessments meeting the definition of a positive pruritus assessment at the subject level over the 24-week Treatment Period. A positive pruritus assessment includes an itch score  $\leq 1$ , or at least a one-point drop from baseline based on the Albireo PRO instrument; only patients  $\geq 8$  years of age will complete the Albireo PRO instrument
- Proportion of individual assessments meeting the definition of a positive pruritus assessment at the subject level from Weeks 0-4, Weeks 0-8, Weeks 0-12, Weeks 0-18, Weeks 0-24, respectively, or the proportion of positive pruritus assessments at each 4-week interval.
- Proportion of individual AM assessments meeting the definition of a positive pruritus assessment at the subject level from Weeks 0-4, Weeks 0-8, Weeks 0-12, Weeks 0-18, Weeks 0-24, respectively, or the proportion of positive pruritus assessments at each 4-week interval.
- Proportion of individual PM assessments meeting the definition of a positive pruritus assessment at the subject level from Weeks 0-4, Weeks 0-8, Weeks 0-12, Weeks 0-18, Weeks 0-24, respectively, or the proportion of positive pruritus assessments at each 4-week interval.
- Number of patients undergoing biliary diversion surgery or liver transplantation

### 9.1.3 Exploratory Efficacy Endpoints

Exploratory efficacy endpoints are compared to placebo and include the following:

- Assessment of Global Symptom Relief at Weeks 4, 12, and 24 as measured by patient, caregiver, and clinician via the PGIC items ([Appendix 3](#))
- Change from baseline in fasting s-BA at Week 4

- Change in pruritus, as indexed by caregiver-reported observed scratching, from baseline by each 4 week-interval of the Treatment Period as measured by the Albireo ObsRO instrument
- Change from baseline by each 4-week interval of the Treatment Period in patient-reported and observer-reported night time itching and scratching severity scores, respectively
- Change from baseline by each 4-week interval of the Treatment Period in patient-reported and observer-reported morning time itching and scratching severity scores, respectively
- Change from baseline by each 4-week interval of the Treatment Period in pooled pruritus score including observer-reported scratching for patients <8 years of age and patient-reported itch severity for patients  $\geq 8$  years of age
- Change from baseline by each 4-week interval of the Treatment Period in additional patient-reported and observer-reported sleep parameters (e.g., tiredness and number of awakenings)
- Change from baseline to Week 24 in PedsQL ([Appendix 4](#))
- Change from baseline in serum ALT concentration at Week 4
- Change from baseline in total bilirubin at Weeks 4, 12, and 24
- Change from baseline in AST and GGT at Weeks 4, 12, and 24
- Change from baseline for other biochemical markers and measures of bile acid synthesis (autotaxin, p-C4) at Week 24
- Change in pediatric end-stage liver disease/model for end-stage liver disease (PELD/MELD) score, AST to platelet ratio index (APRI) score, and Fib-4 score from baseline to Week 24
- Change from baseline to Week 24 in stage of liver fibrosis as assessed by Fibroscan® (where available)
- Liver-related mortality and liver decompensation events
- All-cause mortality

## **9.2 Efficacy Assessments**

### **9.2.1 Serum Bile Acids**

Blood samples for analysis of fasting total s-BA will be drawn at all visits. Patients will fast (water intake only is permissible) for at least 4 hours prior to the collection of samples for s-BA. Exceptions can be made for infants, <12 months of age, if unable to fast for the full 4 hours. Any visit at which a bile acid sample result is unreportable, an additional unscheduled visit for a repeat sample collection may be scheduled. All s-BA results during

the treatment period and follow-up will be blinded. Samples will be processed and transported to a central laboratory per instructions in the laboratory manual.

### **9.2.2 Itching, Scratching and Sleep Score**

Itching, observed scratching, and sleep disturbance will be recorded twice each day via eDiary. Patients and/or caregivers will be instructed to complete the eDiary every day in the morning after the patient wakes and in the evening just before the patient goes to sleep throughout the study. Patients and caregivers will receive a formal training session during Visit 1.

The eDiary includes Albireo ObsRO and PRO items. Patients <8 years of age will not be asked to complete the Albireo PRO items; only the Albireo ObsRO will be completed by caregivers of patients in this age group. Older patients, 8 to 18 years of age, will complete the Albireo PRO items and the caregiver will complete the Albireo ObsRO items. The Albireo PRO items assess severity of itch, aspects of sleep disturbance (morning diary only), and tiredness. For patients 8 to 12 years of age, the caregiver will read the Albireo PRO items along with the child and record the child's response. A guide will be provided to the caregivers that provides standardized explanations of the Albireo PRO items, in case the patient is confused or requires clarification about the meaning of a question. The Albireo ObsRO items assess severity of observed scratching, aspects of observed sleep disturbance (morning diary only), and observed signs of tiredness (evening diary only). The Albireo ObsRO and PRO scratching and itch severity items use 0 to 4 response scales, where each response is distinguished by a unique facial expression, verbal anchor, number, and color code ([Appendix 2](#)). To meet eligibility criteria, a scratch score will be calculated from daily diary entries (ObsRO items) the 14 consecutive days prior to randomization.

A daily AM & PM score for the Albireo ObsRO scratching item will be averaged from the 2 ratings for each day. A daily score will be considered missing if both of the daily assessments are missing. A weekly score will be calculated by averaging the daily scratching scores. A weekly score will be considered missing if  $\geq 4$  out of 7 days a week of data are missing. For AM & PM baseline, a 14-day daily score of AM & PM prior to the first dose of study medications will be averaged as the baseline score.

For AM baseline, a 14-day AM score prior to the first dose of study medications will be averaged as the AM baseline score. The same approach will be used for PM baseline and to calculate a patient-reported itch severity score. The handling of missing data is described in [Section 11.2.2.2](#).

### **9.2.3 Growth**

Growth will be measured as height (velocity) and weight (Z-score) using a certified weight scale. BMI will be calculated by weight (kg) / height (m). Change will be defined as linear growth deficit (weight and BMI for age) compared to a standard growth curve (Z-score, SD from P50).

#### 9.2.4 Quality of Life Questionnaire (PedsQL)

Patients and caregivers will be asked to complete a QoL questionnaire (PedsQL) at Visit 3 and Visit 9. Details of the questions included on the questionnaire are provided in [Appendix 4](#).

#### 9.2.5 Biomarkers and PK Samples

Blood samples for autotaxin and p-C4 will be drawn at Visits 3, 4, and 9 only for children with body weight >10 kg. Blood for A4250 PK assessment will only be drawn at Visits 4 and 9 (only for children with body weight >10 kg), and as close to the onset of an SAE as possible, should an SAE occur. Samples will be processed and transported to a laboratory per instructions in the laboratory manual.

#### 9.2.6 PELD/MELD Score

At randomization and end of treatment, PELD score will be calculated for children up to 12 years of age. For children 13 years or older, the MELD score will be calculated.

PELD Score =  $4.80 * \ln(\text{total bilirubin}) + 18.57 * \ln(\text{INR}) - 6.87 * \ln(\text{albumin}) + 4.36$  (if patient <1 year: scores for patients listed for liver transplantation before the patient's first birthday continue to include the value assigned for age (<1 year) until the patient reaches the age of 24 months) + 6.67 (if the patient has growth failure [ $\leq 2$  SD])

Laboratory values less than 1.0 will be set to 1.0 for the calculation of the PELD score.

MELD Score =  $9.57 * \ln(\text{creatinine}) + 3.78 * \ln(\text{total bilirubin}) + 11.2 * \ln(\text{INR}) + 6.43$

Laboratory values less than 1.0 will be set to 1.0 and serum creatinine values greater than 4.0 mg/dL (equivalent to 353.6  $\mu\text{mol/L}$ ) will be set to 4.0 for calculation of the MELD score.

#### 9.2.7 Fibroscan®

Where available, Fibroscan® will be performed as per institution standard practice at Visits 3 and 9.

#### 9.2.8 Markers of Fibrosis

APRI score and Fib-4 score will be calculated at randomization and at end of treatment.

APRI =  $[(\text{AST in U/L}) / (\text{AST ULN in U/L})] / (\text{Platelets in } 10^9/\text{L})$

Fibrosis 4 Score =  $(\text{Age} * \text{AST in U/L}) / (\text{Platelets in } 10^9/\text{L} * \sqrt{(\text{ALT in U/L})})$ .

#### 9.2.9 Global Impression of Change and Global Impression of Symptom Measures

Patients ( $\geq 8$  years of age), caregivers, and clinicians will complete the PGIC and the PGIS measures ([Appendix 3](#)) at randomization (Visit 3; PGIS only), Visits 4 and 6, and at EOT (Visit 9).

The PGIC items assess change in itch (patient version), scratching (caregiver and clinician versions), and sleep (all versions) since starting the study drug. The PGIS items assess itch

(patient version), scratching (caregiver and clinician versions), and sleep (all versions) in the past week. Caregivers and clinicians will complete the PGIC and PGIS for all patients; those patients  $\geq 8$  years of age will complete the patient version.

## 10 ASSESSMENT OF SAFETY

The timing and frequency of safety assessments are described in [Section 7.1.3](#) and in [Table 1](#) above.

The primary safety analysis for this study will include the incidence of total treatment-emergent adverse events (TEAE) and TEAEs categorized by causality, severity, and seriousness assessments made by the investigator by comparing study drug exposure to placebo.

Trends in safety will also be evaluated for the following assessments:

- Physical examinations
- Concomitant medications
- Vital signs
- Laboratory test results (including clinical chemistry, hematology, urinalysis, AFP, and vitamins A and E, 25-hydroxy vitamin D, and INR)
- Abdominal ultrasound
- Discontinuations due to AEs

### 10.1 Adverse Events

#### 10.1.1 Definitions and Investigator Assessments

An AE is defined as any untoward medical occurrence in an enrolled patient regardless of causal relationship with study drug. An AE can therefore be any clinically significant unfavorable and unintended sign, symptom, or disease that occurs once a patient is enrolled (ICF is signed) in the study until the patient is discharged from the study, whether or not related to the study drug.

##### 10.1.1.1 Clinical Significance

Clinical significance is defined as any abnormal finding that results in further clinical investigation(s), treatment(s), or the diagnosis of new condition. Patient-reported events and protocol-mandated laboratory values, vital signs, and physical examination findings can be considered clinically significant (i.e., an AE) if there is a deterioration as compared to baseline. Examples of clinically significant worsening from baseline could include, but is not limited to, events causing withdrawal from the study and events requiring medical intervention outside of the study causing apparent clinical manifestations, or judged relevant by the investigator.

##### 10.1.1.2 Serious Adverse Events

Serious criteria are applied by the investigator to each AE as specifically defined below. These criteria are used to determine whether an AE is serious or non-serious. The assessment

is made independently of severity assessment ([Section 10.1.1.3](#)). For example, the development of a severe rash that occurs after signing of informed consent may not meet serious criteria as defined below and therefore would be considered a severe, non-serious AE.

Any AE that meets any 1 of the following 6 criteria is considered an SAE:

- The outcome of the AE is **death**
- The AE is immediately **life-threatening**. Life-threatening means that the patient is, in the opinion of the investigator, at immediate risk of death from the reaction as it occurred. This does not include an AE that, if more severe, might have caused death
- The AE results in persistent or significant **disability/incapacity**. Disability means a substantial disruption of a person's ability to conduct normal life functions
- The AE requires or prolongs **hospitalization**
- The AE results in a **congenital anomaly/birth defect**
- **The AE is an important medical event**. Important medical events may meet serious criteria should the investigator assess that they may significantly jeopardize the patient, represent a significant hazard, or requires medical/surgical intervention to prevent one of the outcomes listed above. Examples of potential SAEs based on this criteria include, but are not limited to, allergic bronchospasm requiring intensive treatment in an emergency room or at home, blood dyscrasias or convulsions even if they do not result in inpatient hospitalization, or the development of drug dependency and drug abuse.

#### 10.1.1.3 Severity Assessment

Severity assessments are based on the intensity of the event in relation to expectation. The investigator will assess the intensity of AEs based on the following definitions:

- Mild (awareness of sign or symptom, but easily tolerated)
- Moderate (discomfort sufficient to cause interference with normal activities)
- Severe (incapacitating, with inability to perform normal activities)

Severity is a measure of intensity where seriousness is defined by the criteria outlined in [Section 10.1.1.2](#). An AE of severe intensity need not necessarily be considered serious. For example, nausea that persists for several hours may be considered severe nausea, but not meet serious criteria, and therefore would be assessed as a severe AE but not an SAE.

#### 10.1.1.4 Causality Assessment

The investigator determines the causality of all AEs to the study drug using medical judgment and considering all relevant factors such as (but not limited to) the underlying study indication, coexisting disease, concomitant medication, relevant history, pattern of the AE, temporal relationship to the study drug, and de-challenge or re-challenge. The causality assessment of the AE/SAE is to be made as follows.

### **Related to study drug (possibly, probably, or definitely related)**

Based on medical judgment, there is at least a reasonable possibility that the study drug caused the event; one or more of the following criteria apply:

- The event follows a reasonable temporal sequence from administration of study drug
- The event could not be reasonably attributed to the known characteristics of the patient's clinical state, environmental or toxic factors, or other modes of therapy administered to the patient
- The event follows a known pattern of response to study drug
- The event disappears or decreases on cessation or reduction in dose of the study drug. (It should be noted that in some situations an AE will not disappear or decrease in intensity upon discontinuation of study drug despite other clear indications of relatedness)
- The event reappears or worsens when the study drug is re-administered

### **Unrelated to study drug (unlikely or unrelated)**

Based on medical judgment there is no reasonable possibility that the study drug caused the event; one or more of the following criteria apply:

- The event does not follow a reasonable temporal sequence from administration of study drug
- The event could be reasonably attributed to the known characteristics of the patient's clinical state, concurrent illness, environment or toxic factors, or other modes of therapy administered to the patient
- The event does not follow a known pattern of response to study drug
- The event does not disappear or decrease on cessation or reduction in dose of the study drug, and it does not reappear or worsen when the study drug is re-administered

### **10.1.2 Recording of Adverse Events**

It is the investigator's responsibility to assess whether each untoward event is a clinically significant worsening from baseline, thereby considered an AE. For all AEs, the severity, seriousness, and causality to study drug for each AE as outlined in [Section 10.1.1](#) will be assessed and recorded in the eCRF.

All serious and non-serious AEs are collected once the caregiver/patient has signed the ICF and until the post-treatment follow-up (Visit 10) or 28 days after the last dose of study drug.

Any AEs or SAEs that are unresolved at the patient's last AE assessment in the study are followed up by the investigator until resolution or stabilization up to the database lock and recorded in the eCRF. Albireo retains the right to request additional information for any patient with ongoing AE(s) or SAE(s) at the end of the study.

TEAEs are defined as any AE that occurs after randomization (Day 0). All AEs that occur in the Screening Period, i.e., after enrollment and prior to randomization, will be collected on the eCRF as non-treatment-emergent AEs.

If there is a clinically significant deterioration of a laboratory value/vital sign or other routine study assessment that is associated with a diagnosis, the clinical diagnosis will be reported as an AE and the associated signs and symptoms will be considered additional information unless the sign or symptom is more severe than expected given the diagnosis. For example, if an investigator diagnoses a study patient with hepatitis during the study period, hepatitis would be considered the AE and the concomitant signs and symptoms of abdominal pain, vomiting, and elevated ALT and AST would not be reported separately unless, in the opinion of the investigator, one of these signs or symptoms is more severe than expected and therefore a separate AE assessment is indicated.

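### Sections 10.1.1, 10.1.1.1 and 10.1.2 of the protocol set conflicting thresholds for recording an adverse event, so sites may record or omit the same mild, untreated symptom

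*Protocol*

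**What the plan says.** All references are to the current protocol, dated 24 June 2019. The versions of 29 April 2019 and 1 March 2019 carry the same wording.

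- **Section 10.1.1, first sentence:** "An AE is defined as any untoward medical occurrence in an enrolled patient regardless of causal relationship with study drug". No threshold is attached.
- **Section 10.1.1, second sentence:** "An AE can therefore be any clinically significant unfavorable and unintended sign, symptom, or disease". A significance condition now appears.
- **Section 10.1.1.1, first sentence:** "Clinical significance is defined as any abnormal finding that results in further clinical investigation(s), treatment(s), or the diagnosis of new condition".
- **Section 10.1.1.1, second sentence:** events that patients report, along with scheduled laboratory, vital-sign and examination findings, "can be considered clinically significant (i.e., an AE) if there is a deterioration as compared to baseline".
- **Section 10.1.1.1, third sentence:** an open list of examples that ends with events "or judged relevant by the investigator".
- **Section 10.1.2, the recording rule:** the investigator must "assess whether each untoward event is a clinically significant worsening from baseline, thereby considered an AE". Severity, seriousness and causality are then recorded for the events that count as AEs.
- **Section 10.1.1.3:** the lowest severity grade reads "Mild (awareness of sign or symptom, but easily tolerated".
- **Section 10:** "The primary safety analysis for this study will include the incidence of total treatment-emergent adverse events (TEAE". The comparison is with placebo and is broken down by causality, severity and seriousness.

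**The concern.** The recording rule in 10.1.2 applies a clinical-significance test to every untoward event, symptoms included, before the event becomes an AE. The only sentence that defines clinical significance ties it to something being done about the event or a new condition being diagnosed. A mild, easily tolerated symptom often leads to neither. The opening definition would count it and the severity scale has a grade for it, but the recording rule, read with that definition, would drop it.

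This matters more than usual here. Section 5.3.1 says that loose stools or diarrhea could be expected from the drug's mode of action, and the one case it cites from the pediatric Phase 2 study was mild and transient. Such events are the ones most exposed to the ambiguity, and TEAE incidence is the primary safety analysis. The loss would occur at data collection. An event judged not to be an AE is not entered as one, so no analysis plan can restore it. The eDiary described in 9.2.2 covers itching, scratching, sleep and tiredness, not stools, and so offers no second source.

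**Working it through.** No formula settles this point, and there is no plan figure to reproduce. The check is to follow one event through the text.

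**Test case.** A child without loose stools at baseline has a short episode after randomization. There is no work-up, no treatment and no new diagnosis.

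| Section | Status of the event |
|---|---|
| 10.1.1, sentence 1 | An AE; no threshold applies |
| 10.1.1, sentence 2 | An AE if clinically significant; silent on the alternative |
| 10.1.1.1, sentence 1 | Not clinically significant: no investigation, treatment or new diagnosis |
| 10.1.2 with 10.1.1.1, sentence 1 | Not an AE |
| 10.1.1.1, sentence 2 | May be an AE, because it is a deterioration from baseline |
| 10.1.1.1, sentence 3 | May be an AE, if the investigator judges it relevant |
| 10.1.1.3 | Can be graded Mild, which presupposes that it was recorded |
| 10.2.2.4 (diarrhea) | Not reached: that section concerns diarrhea with a listed accompanying sign or lasting 7 or more days |

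The result is three thresholds: one that requires recording, one that rules it out, and one that leaves it to discretion. Two sites can each point to the protocol and record this child differently.

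**Does it reach the primary safety result?**

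1. Section 10.1.2 defines a TEAE as any AE after randomization, so a TEAE inherits whatever threshold was used for the AE.
2. Section 10 makes TEAE incidence the primary safety analysis.
3. Section 11.2.2.7 tabulates TEAEs by intensity, and 11.2.4 has the DSMB review AE data.

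The ambiguity therefore carries into the main safety tables and the monitoring.

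**Direction.** Let p_A and p_P be the true incidences of one type of event on A4250 and placebo. Let f be the share of affected children whose episodes are all mild, without consequence and left out. Blinded investigators would apply the same rule in every arm, so take a common f.

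- Recorded difference = (p_A − p_P)(1 − f), which is smaller than the true difference when p_A > p_P.
- Recorded ratio = p_A(1 − f) / [p_P(1 − f)] = p_A / p_P, which is unchanged.

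Recorded incidence falls in both arms. The absolute difference shrinks only if the event is commoner on A4250.

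**Granularity.** The plan has 20 children per arm (7.1.1). One child left out moves an arm's incidence by 1/20 = 5 points, and two move it by 2/20 = 10 points. For total TEAEs this holds only if the child has no other recorded TEAE.

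**The case against.** The best reply is that 10.1.1.1 has to be read whole. Its second sentence names patient-reported events and gives them another test, deterioration from baseline, and the phrase about worsening in 10.1.2 matches that test. New loose stools pass it. The second sentence of 10.1.1 does not restrict AEs to clinically significant events; it only says what an AE can be. The Mild grade, the statement that serious and non-serious AEs alike are collected, and AE monitoring at every clinic visit and the Day 14 call all point to inclusive recording. Assessment is blinded, and the protocol and eCRF are reviewed with investigators before a site starts (13.2).

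Much of this stands. A reader might infer that the protocol excludes mild diarrhea from the AE count. It does not: recording it is left to discretion. The objection fails on one point. The wider routes are permissive, so they allow a mild event to be recorded without requiring it, and they add a further standard to the two that already conflict.

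Three other strong inferences are not supported.

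- **The Phase 2 diarrhea case.** A reader might count it as 1 of 20 under one rule and 0 of 20 under the other. The protocol does not say whether that case had a work-up or treatment. It was also reported, under a different protocol.
- **Sizing the loss.** With assumed diarrhea rates of 30% and 10%, (0.30 − 0.10)(1 − f) gives 20 points at f = 0, 10 at f = 0.5 and 4 at f = 0.8. Neither the rates nor f come from the documents. The ratio stays at 3 throughout. The figure concerns diarrhea, not total TEAEs, to which a child with any other recorded TEAE still contributes.
- **Site behavior.** Up to 50 sites are planned, but nothing shows that they will under-record. The text permits it, and no more than that can be said.

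The comparison with baseline in 10.1.2 also has a proper purpose. Inclusion criterion 4 requires significant pruritus, and 5.2.1 describes jaundice and raised transaminases as common in this disease. TEAEs are defined by timing alone. Without a worsening test, unchanged chronic disease could be counted as TEAEs in every arm.

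**Conclusion.** The concern holds as a conflict of wording with a real consequence for data collection. Sections 10.1.1, 10.1.1.1 and 10.1.2 give no single recording threshold, and a site can omit a mild, untreated symptom without departing from the protocol. The severity scale and the primary safety analysis both presuppose that such events are recorded.

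The effect cannot be sized, because the documents give no rate of mild, untreated events in either arm. Any omission would lower recorded incidence. It would shrink the absolute difference from placebo only on the assumption that mild events are commoner on A4250, which section 5.3.1 makes plausible for loose stools but does not establish. With 20 children per arm, a few unrecorded cases would be visible in the tables. The point should be corrected. It does not show that the safety results are biased.

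**What to change.** Reconcile 10.1.1, 10.1.1.1 and 10.1.2 to one threshold:

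1. Any untoward sign, symptom or disease that is new or worse than at baseline after consent is recorded as an AE, whatever its severity and whether or not it led to investigation or treatment.
2. The clinical-significance test of 10.1.1.1 applies only to laboratory values, vital signs and examination findings that the protocol schedules.

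Keep the comparison with baseline, for the reason given under the objection. The change concerns recording only and leaves the management rules of 10.2.2 as they are.

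The cost is a wording amendment and a short instruction to sites. The downside is more mild AEs to record and code, and somewhat higher reported AE rates.
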